9.3 Concomitant medication/treatment

A concomitant medication is any medicatiom, other than the trial product, which is taken during the trial. Details of any concomitant medication must be recorded at visit 1. Changes in concomitant medication must be recorded at each subsequent visit as they occur.

Concomitant medications that are not permitted during the study period

Plasma levels and efficacy of prednisolone may be affected by the concomitant use amphotericin B, anticholinesterase agents, CYP 3A4 inducers (e.g. barbiturates, phenytoin, carbamazepine, and rifampin), CYP 3A4 inhibitors (e.g., ketoconazole, macrolide antibiotics), cyclosporine and digitalis. Lithium, Propylthiouracil, Lugols iodine, Contrast medium are not permited as it will affect the results of the study.

Cautious use of phenylbutazone, warfarin, thiazide diuretics (acidic) as well as tetracycline penicillin G, phenobarbital, thyroid and thyroxine preparations, estrogens and progestins and digitalis as cholestyramine resin may delay or reduce the absorption of these drugs.

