 - If hypothyroidism occurs during study treatment, stop study treatment and repeat thyroid function test one week later. Thyroid function tests will be reviewed and medication adjusted. All adjustment to medications will be documented in CRF. No thyroxine will be given as hypothyroid will recover upon discontinuing study treatment. Subject will discontinue study treatment if develop persistent and severe profound symptoms of hypothyroidism
- 6. Hyperthyroid and thyroid storm
 - If subjects are still hyperthyroid (no reduction in Free T4 and Free T4 from baseline) at the end of week 4, Carbimazole will be increased in accordance to the standard practice. In the event if subjects are symptomatic of thyrotoxicosis throughout trial period, propanolol doses may be increased as per clinician judgement and documented in CRF. In the event that subject develops thyroid storm during trial period, SAE will be reported, study treatment discontinued and treatment of thyroid storm with lugol's iodine, beta blockers, hydrocortisone and high doses of propylthiouracil will be initiated as per standard practice.

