11.2 Criteria for stopping subject treatment

The investigator will discontinue a subject's taking of study treatment at any time if the subject:

1. Who no longer wishes to participate in the trial and wishes to withdraw from the study at any time

2. Experiences intolerable adverse reactions

3. Is diagnosed with any of the exclusion criteria during the intervention period

4. Develops hypothyroid during the intervention period (Hypothyroid is defined as symptoms of hypothyroidism coupled with elevated TSH > 4.7 mU/L and normal or low levels of Free T4 <9 pmol/L

In all these cases, the investigator and/or the treating physicial will if possible encourage the subject to continue with the follow up assessment and to allow the use of collected data in the analyses.

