13 STATISTICAL METHODS

13.1 Sample size and power considerations

The sample sizes estimations and analyses plan were made with the caveat that the three-treatment groups comparison is as little difference from carrying out a series of three independent trials, and to use conventional significance tests without adjustment as argued by Saville (1990)²⁰. Sample size and power considerations

Sample sizes were estimated by using PASS 11 software²¹. The estimations were based on primary objectives only.

Primary objective: To achieve 80% power to detect a 30% difference in the proportions achieving normal FT_4 between Group 3 (Carbimazole+Propanolol) and each of Group 1 (Cholestyramine + Carbimazole+ Propanolol) and Group 2 (Prednisolone+ Carbimazole+ Propanolol), 41 patients are needed in each group. The proportion achieving normal FT_4 in Group 3 was estimated to be 40%. (1) Allowing for 10% drop out rate, the sample size required is therefore 45 per arm. The test statistic used is the two-sided Z test with pooled variance.

The significance level was targeted at 0.05.

Primary objective: To achieve 80% power to detect a 30% difference in the proportions achieving normal FT_3 between Group 3 (Carbimazole+Propanolol) and each of Group 1 (Cholestyramine + Carbimazole+ Propanolol) and Group 2 (Prednisolone+ Carbimazole+ Propanolol), 41 patients are needed in each group. The proportion achieving euthyroid status in Group 3 was estimated to be 40%. (1) Allowing for 10% drop out rate, the sample size required is therefore 45 per arm. The test statistic used is the two-sided Z test with pooled variance. The significance level was targeted at 0.05.

Thus, the final sample size will be 45 per group.

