13.2.2 Efficacy Analysis

1. For the primary objectives, all comparisons of means between treatment will be analysed using one-way ANOVA and all pairwise comparisons of proportions will be analysed by using two-sided Z test and 95% confidence interval of the estimated difference will be calculated. Alpha level will be set at 0.05 and no adjustment will be made for the multiple pairwise comparisons. Analysis will be based on intention to treat and per protocol analysis.

2. For secondary objectives, all comparisons of means between treatment will be analysed using one-way ANOVA and all comparison of proportions will be analysed using chi-square test of independence.

Alpha level will be set at 0.05. Analyses will be based on safety set analysis.

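### As written, a subject rescued for thyroid storm with Lugol's iodine and propylthiouracil would be scored a success of the assigned arm if FT4 or FT3 is then normal, although section 9.3 says these agents affect the results

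*Combined protocol and SAP*

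**What the plan says.** - **Endpoint (9.8 and synopsis).** The primary endpoint is the proportion with a normal free T4 or free T3 at 2 and 4 weeks. It carries no condition on the treatment received before the reading.
- **Rescue (10.4, item 6).** If thyroid storm develops, study treatment is discontinued and "treatment of thyroid storm with lugol's iodine, beta blockers, hydrocortisone and high doses of propylthiouracil will be initiated as per standard practice".
- **Barred agents (9.3).** "Lithium, Propylthiouracil, Lugols iodine, Contrast medium are not permited as it will affect the results of the study". This sentence does not name hydrocortisone. Synopsis exclusion 15 does list hydrocortisone as a steroid compound, alongside prednisolone, which is Group 2's adjunct.
- **After stopping (8.4.3, 8.4.4, 11.2).** Storm is an exclusion criterion (8.4.2, item 19). A subject who develops it therefore meets the withdrawal condition in 8.4.3 and the stopping criterion in 11.2, item 3. Section 8.4.4 encourages withdrawn subjects to keep attending visits. For subjects who stop treatment, 11.2 has the investigator, if possible, "encourage the subject to continue with the follow up assessment and to allow the use of collected data in the analyses".
- **Analysis (13.2.2).** "Analysis will be based on intention to treat and per protocol analysis". Neither set is defined there or in 13.2.

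No section says whether a reading taken after rescue counts as normal, not normal or missing.

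**The concern.** The sponsor's own text says that Lugol's iodine and propylthiouracil distort the measured outcome. Yet the plan has no rule to stop a reading taken under those drugs from being credited to the assigned regimen. Storm during treatment is the clearest failure of hormone control in this trial, and the literal scoring can turn it into a success. Hydrocortisone adds a second difficulty: rescue gives a subject in Group 1 or Group 3 a steroid, the drug class that Group 2 is meant to test.

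The protocol's hypothesis is that the adjuncts reach euthyroidism more effectively and faster. If so, failures should be more frequent in Group 3, and rescue successes would raise the control proportion and shrink both adjunct effects. The per-protocol analysis is not a remedy. If its undefined set drops these subjects, failures are removed rather than counted. The trial is open label, so a choice made after the data are seen would be made with the arms known.

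**Working it through.** **Inputs from 13.1.** "To achieve 80% power to detect a 30% difference in the proportions achieving normal FT_4 between Group 3" and each adjunct group; 40% in Group 3, hence 70% in an adjunct group; 41 per group, 45 after 10% dropout. "The test statistic used is the two-sided Z test with pooled variance". Two-sided alpha is 0.05.

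**Inputs not in the documents.** The rescue rate, its split by arm, and the proportion normal after rescue. These are assumed below.

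**Step 1. Reproduce the plan's figure.** With p1 = 0.40, p2 = 0.70 and mean 0.55:

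n = [1.96 × √(2 × 0.55 × 0.45) + 0.842 × √(0.40 × 0.60 + 0.70 × 0.30)]² / 0.30² = 41.97, so 42 per group.

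Exact binomial enumeration of the pooled Z test gives 79.6% power at 40 and 81.3% at 41, which matches the stated 41. For dropout, 41 / 0.9 = 45.6, against the stated 45. The differences do not matter here.

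**Step 2. Power formula.** With m the mean of p1 and p2:

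power = Φ{[(p2 − p1)√n − 1.96 √(2m(1 − m))] / √(p1(1 − p1) + p2(1 − p2))}.

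At 0.40 v 0.70 this gives 82.8% at 45 per arm and 79.0% at 41.

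**Step 3. Rescue in Group 3 only.** Let k Group 3 subjects be rescued, all with a normal reading afterwards. Each adds 1/45 = 2.2 points, so p1 = 0.40 + k/45, with p2 held at 0.70. The 41-per-arm column uses the same rates with the smaller n.

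| k | Group 3 rate | Difference | Power, 45 per arm | Power, 41 per arm |
|---|---|---|---|---|
| 0 | 40.0% | 30.0 points | 83% | 79% |
| 1 | 42.2% | 27.8 points | 77% | 73% |
| 2 | 44.4% | 25.6 points | 69% | 65% |
| 3 | 46.7% | 23.3 points | 62% | 57% |

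**Step 4. Equal rescue.** If 5% of each arm is rescued and all normalise, the rates are 45% v 75%: the difference is still 30 points and power is 84.0% at 45 per arm. At 10% in each arm they are 50% v 80%, with power 86.0%. The comparison loses nothing.

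**Step 5. One subject near the boundary.** With 18/45 v 28/45, pooled z = 2.11 and p = 0.035. Scoring one rescued Group 3 subject as normal gives 19/45 v 28/45, z = 1.90 and p = 0.058.

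**The case against.** The strongest reply has four parts.

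1. **The scoring is an inference.** A reader might infer that the plan declares rescued subjects to be successes. It does not. Section 11.2 only encourages continued follow-up and use of data, and with undefined sets such a subject could be treated as withdrawn or missing. This stands as a limit on the wording. It does not remove the problem, because no rule supports those alternatives either, and endpoint plus intention to treat points to the observed value.
2. **Reach is small.** Storm at entry is excluded, every arm receives carbimazole and propranolol, and storm is the only described route to the agents 9.3 says affect the results. The carbimazole increase in 10.4 comes at the end of week 4, the last efficacy visit, so a reader should not infer that ordinary escalation contaminates the endpoint. This stands.
3. **Using values regardless of rescue is a recognised intention-to-treat approach, and here it is conservative for adjunct against standard treatment.** Both are fair if failures do concentrate in Group 3. But the plan does not say it chose that approach, and it sits badly with the statement in 9.3.
4. **A rule scoring every barred agent as failure would overreach.** Incidental contrast, or a steroid given for another reason, is no sign of lost hormone control, and an open-label prescribing decision would then fix the outcome. This stands, and it limits the fix to rescue after study treatment has been stopped. Some open-label discretion remains even so, which is why the observed-value analysis should be shown too.

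**Conclusion.** The point holds as a minor gap. The literal combination of 9.8, 10.4, 11.2 and 13.2.2 credits the assigned arm with a normal FT4 or FT3 reached under Lugol's iodine and propylthiouracil, which 9.3 says affect the results.

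The size runs from no change in the 30-point difference, if rescue is balanced, to a loss of 2.2 to 6.7 points if one to three subjects are rescued in Group 3 only and all normalise. In the second case power falls from 83% to about 77%-62% at 45 per arm, or from 79% to about 73%-57% at 41. That is a one-sided illustration, not an expected loss: the documents give no rescue rate, and the concentration of failures in Group 3 is plausible but not documented.

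Two wider readings are not supported. A reader might infer that 9.3 names hydrocortisone as affecting the results, but its sentence does not; the concern there is only that it is a steroid, like Group 2's adjunct. A reader might also extend the point to other antithyroid agents given after withdrawal for any reason, but no section describes such treatment.

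**What to change.** Add to 13.2.2:

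- In the primary intention-to-treat analysis, a subject who had study treatment stopped and received rescue antithyroid therapy (Lugol's iodine, propylthiouracil or lithium, including the storm regimen in 10.4) before a reading is classed as not normalised at that reading.
- The analysis of observed values regardless of rescue is shown as a sensitivity analysis.
- The number rescued is reported by arm.
- Incidental contrast, or a steroid given for an unrelated reason, is handled only in a sensitivity analysis and is not scored as failure.

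Define the intention-to-treat and per-protocol sets in the same place, and reconcile 9.3 with 10.4, since one bars agents that the other provides for. All readings should still be collected.

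The cost is a short addition to the text and one table row. Section 9.3 already requires medication changes to be recorded at each visit, and 11.1.4 repeats this for weeks 2 and 4, so no new data are needed. The downside is that response rates may look slightly lower. No change to rescue care is proposed.

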10.5 Safety update

Any safety updates will be notified to MREC

11 STUDY CONDUCT

11.1 Study visits and procedures

11.1.1 Screening visit (Week -1, Visit 1)

- 1. Screening of all overt hyperthyroid subjects due to Graves disease
- 2. Assess subject for eligibility to enter study according to the inclusion and exclusion criteria.
- 3. Obtain written consent from subject or parent/guardian.
- 4. Obtain medical history
 - a. Hyperthyroid history
 - b. Past medical history
 - c. Cardiovascular complications of hyperthyroidism
 - d. Family history of thyroid disease
 - e. Smoking history
 - f. Medication history
- 5. Perform baseline measurements of vital signs (BP, HR, Temperature) and anthropometric measurements (Height (cm), Weight (kg) and BMI)
- 6. Perform complete examination including
 - a. Presence of Graves Opthalmopathy and disease activity
 - b. Thyroid examination
 - c. Cardiovascular examination including presence of atrial fibrillation
- The following screening tests are done (Total of 10 mls of blood will be sampled). All screening blood tests will be sent to **respective site's own** laboratory for analysis.
 - a. Free T₄, Free T₃, TSH
 - b. Hep Bs Ag, Anti HCV ab, HIV1/2 ab
 - c. FBS/RBS
 - d. FLP
 - e. Liver function test
 - f. Renal function test

- g. FBC
- h. UPT (For all women of childbearing age)
- 8. Record all screened subjects in the Screening Log regardless of whether or not the subject has been enrolled in the study.
- 9. Refer to the study activities table below.

11.1.2 Baseline visit (Week 0, Visit 2)

- Subjects who are eligible for the study after reviewing both inclusion and exclusion criteria will be called up for a baseline visit no longer than 1 weeks from screening visit.
- 2. Perform baseline measurements of vital signs (BP, HR, Temperature) and anthropometric measurements (Height (cm), Weight (kg) and BMI
- 3. Perform complete medical history and physical examination if not done during screening visit
- 4. Record any concomitant medications
- 5. The following baseline tests will be performed (Total of 6 mls of blood will be sampled). Thyroid function test and TRAb levels will be sent to central lab (Gribbles laboratory) whereas the other tests will be conducted at respective site.
 - a. Free T₄, Free T₃, TSH
 - b. TRAb levels
 - c. UPT (For all women of childbearing age)
 - d. ECG
 - e. ECHO if evidence of thyrotoxic cardiomyopathy
- 6. Complete relevant section/page of the CRF.
- 7. Subject who has fulfilled all inclusion and exclusion criteria and has completed baseline assessment will proceed to randomisation into any of the 3 treatment groups on the **same day**.
- 8. Refer to the study activities table below

11.1.3 Randomisation

A participant will be randomly allocated to one of the three treatments per random allocation sequence that will be generated by a member of the study team not involved in the subject enrolment and concealed in an envelope.

11.1.4 Study treatment and visits

Study treatment (Visit 3 Week 2)

The investigator will perform the following procedures:

- 1. Medical history taking
- 2. Record any concomitant medication
- 3. Record any change of dose administration of study treatment and assess compliance
- 4. Record any AE or SAE
- 5. Perform physical examination including vital signs (BP, HR, Temperature, Weight)
- Obtain blood sample (total of 6 mls of blood will be sampled). Thyroid function test will be sent to central lab (Gribbles laboratory) whereas the others will be sent to respective site's laboratory. (FT₄, FT₃, TSH, FBS/RBS, Blood urea and serum electrolytes)
- 7. UPT for women of childbearing age
- 8. Complete relevant section/page of CRF
- 9. Dispense study treatment
- 10. Refer to the study activities table below

Study treatment (Visit 4 week 4)

The investigator will perform the following procedures:

1. Medical history taking

- 2. Record any concomitant medication
- Record any change of dose administration of study treatment and assess compliance
- 4. Record any AE or SAE
- 5. Perform physical examination including vital signs (BP, HR, Temperature, Weight)
- 6. Obtain blood sample (total of 6mls of blood will be sampled). Thyroid function test will be sent to central lab (Gribbles laboratory) whereas the others will be sent to respective site's laboratory. (FT₄, FT₃, TSH, FBS/ RBS, Blood urea and serum electrolytes)
- 7. UPT for women of childbearing age
- 8. ECG
- 9. Complete relevant section/page of CRF
- 10. Dispense study treatment
- 11. Refer to the study activities table below

11.1.5 Follow up visit (Visit 5, Week 6)

Safety assessment to monitor for adverse events, monitor for symptoms and signs of adrenal insufficiency and monitor for iatrogenic hypothyroidism.

- 1. Medical history taking
- 2. Perform physical examination including vital signs
- 3. Record any AE or SAE
- 4. Obtain blood sample (total of 6 ml of blood will be sampled). Thyroid function test will be sent to central lab (Gribbles laboratory) whereas the others will be sent to respective site's laboratory. (FT₄, FT₃, TSH, Blood urea and serum electrolytes/ FBS or RBS)

Study Activities Table

	Screening	Baseline Assessment and Randomisation	Treat	ment	Follow up
Visit	1	2	3	4	5
Timeline (wks)	-1	0	2	4	6
Procedures					
Informed consent	Х				
Check eligibility	х				
Blood sample for screening ^a	х				
Randomisation		X			
Patient demographics	Х				
Medical History	х				
Complete physical exam	х				
Height (cm), Weight (kg)	х	Х	х	Х	Х
Vital signs (BP, HR, Weight, Temp)	Х	X	Х	Х	Х
FT ₄ & FT ₃ & TSH	х	X (central lab)	X (central lab)	X (central lab)	X (central lab)
TRAb levels		X (central lab)			
FBS/ RBS	Х		Х	Х	Х
BUSE	Х		Х	Х	Х
UPT ^b	х	X	Х	Х	
U/S Thyroid		Х			
ECG		Х		Х	
ECHO ^c		X			
Efficacy assessment			Х	Х	
Concomitant medication			х	Х	
Report AE and SAE			Х	Х	Х
Dispense study treatment			х	Х	
Assess compliance			х	Х	
Complete relevant section of CRF			X	Х	Х

^a HepBsAg, Anti HCV ab, HIV1/2 ab, FBC, BUSE/Creatinine, LFT, FBS/RBS, FLP. Written consent will be taken for HIV test. All blood tests on screening visit including thyroid function test will be sent to the respective site's laboratory.

^b For women of childbearing age

^c Only if clinically suggestive of thyrotoxic cardiomyopathy or has atrial fibrillation

11.2 Criteria for stopping subject treatment

The investigator will discontinue a subject's taking of study treatment at any time if the subject:

1. Who no longer wishes to participate in the trial and wishes to withdraw from the study at any time

2. Experiences intolerable adverse reactions

3. Is diagnosed with any of the exclusion criteria during the intervention period

4. Develops hypothyroid during the intervention period (Hypothyroid is defined as symptoms of hypothyroidism coupled with elevated TSH > 4.7 mU/L and normal or low levels of Free T4 <9 pmol/L

In all these cases, the investigator and/or the treating physicial will if possible encourage the subject to continue with the follow up assessment and to allow the use of collected data in the analyses.

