8.4.2 Exclusion criteria

- 1. Inability or unwillingness to provide written consent.
- 2. Inability or unwillingness to comply with the requirements of the protocol as determined by the investigator.
- 3. Pregnancy, breastfeeding or use of non-reliable method of contraception.
- 4. Subjects with history of chronic liver disease, chronic renal failure, heart failure, diabetes mellitus
- 5. Subjects with history of peptic ulcer disease, upper gastrointestinal bleeding, diverticulitis or ulcerative colitis.

- 6. Subjects who have recently had live or attenuated virus vaccines
- 7. Subjects with current infection (systemic fungal, active tuberculosis, cerebral malaria, viral hepatitis, HIV)
- 8. Subjects with cataracts and glaucoma
- 9. Subjects with osteoporosis
- 10. Subjects with psychiatric disorders
- 11. Subjects with complete biliary obstruction, bleeding disorders, hypertriglyceridemia (fasting triglyceride levels > 300mg/dL)
- 12. Previous history of adverse reactions to cholestyramine or other bile acid sequestrants
- 13. Previous history of adverse reactions to prednisolone or other steroid compound
- 14. Current use of cholestyramine or prednisolone or other steroid compound
- 15. Participation in another clinical trial and/or receipt of cholestyramine or prednisolone within 4 weeks prior to screening visit.
- 16. Subjects with history of bronchial asthma, bronchospasm, peripheral vascular disease or adverse reactions to propanolol
- 17. Subjects with adverse reactions to carbimazole
- 18. Hypokalemia (serum K^+ <3.5 mmol/L)
- 19. Thyroid storm defined as Burch Wartofsky Score >45

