8.4.3 Subject withdrawal & drop-out

Subjects are free to withdraw from the study at any time for any reason. Subjects may also be withdrawn from the study at any time at the discretion of the investigator. The following are anticipated conditions/events that would require a subject to be withdrawn from the study:

- Adverse reactions or intolerance to study drug
- Protocol violation
- Subject requires use of unacceptable concomitant medication

- Subject not compliant with protocol procedures
- Subject develops a condition during the study that violates the inclusion/exclusion criteria
- Lost to follow-up
- Administrative problems
- Death

8.4.4 **Procedures for handling withdrawal**

Subjects who withdraw or are withdrawn from the study should:

- Have the reason(s) for their withdrawal recorded
- Be asked about the presence of any AEs and if so should be followed up by regular scheduled visits, telephone contact, correspondence or home visits until satisfactory clinical resolution of AEs is achieved.
- Be seen by an investigator and all final assessments will be performed and recorded in the OFF STUDY form.
- Be encouraged to continue coming for regular visits and assessments
- Have at least one follow-up contact (scheduled visit, telephone contact, correspondence or home visit) for safety evaluation during the 30 days following the last dose of study treatment.
- In the event of pregnancy, the subject should be monitored until conclusion of the pregnancy and the outcome of pregnancy reported.
- Have study treatment returned.

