10.4 Treatment and follow up of AE

Treatment of any AE is at the sole discretion of the investigator who should follow up subjects with AE until the event has resolved or until the condition has stabilised. Otherwise appropriate medical care should be arranged for the patient. Abnormal tests should be repeated until they return to baseline levels or an adequate explanation of the abnormality has been found.

- 1. Treatment of over-dosage significant enough to cause adverse effects
 - Study medication must be stopped immediately and subject be monitored closely for all adverse reactions. Immediate thyroid function test to be sent and reviewed.
- 2. Pregnancy
 - A female subject must be instructed to stop taking study medication and immediately inform the investigator if she becomes pregnant during the study. The investigator should counsel the subject and discuss the risks of continuing with the pregnancy and the possible effects on the foetus. Monitoring of the subject should continue until conclusion of the pregnancy. The investigator should report all pregnancies to the coordinating investigator and MREC within 24 hours of being notified of the pregnancy.
 - Pregnancy occurring in the partner of a subject participating in the study should also be reported to the investigator and sponsor. The partner should be counseled and followed as described above.
 Pregnancies will be formally reported as SAEs.
- 3. Hypokalemia
 - If mild hypokalemia (3-3.5 mmol/L), to replace with Mist Potassium Chloride and reassess K⁺ levels after 3 days. If moderate to severe hypokalemia (<3 mmol/L), to assess for symptoms and consider admission for close monitoring, ECG and oral/IV potassium replacement. To consider withdrawing treatment (especially prednisolone) if refractory to active intervention.

- 4. Diabetes
 - To reconfirm by sending a repeat FPG and 2 hour post prandial glucose. Upon confirming diagnosis of diabetes, consider starting oral hypoglycemic drugs. Consider discontinuing study treatment if severe uncontrolled hyperglycemia or hospitalisation for hyperglycemic emergencies.
- 5. Hypothyroid
 - Hypothyroid is defined as symptoms of hypothyroidism coupled with elevated TSH more 4.7mU/L and normal or low levels of Free T4 <9 pmol/L measured during intervention with study drug

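### Sections 11.2 and 8.4.3 require stopping and withdrawal for on-treatment hypokalaemia or new diabetes, section 10.4 says treat and only consider stopping, and no text says which prevails

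*Combined protocol and SAP*

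**What the plan says.** **Exclusion rule.** Criterion 18 in section 8.4.2 is "Hypokalemia (serum K^+ <3.5 mmol/L" (the closing bracket follows). Criterion 4 in the same list covers a history of diabetes mellitus.

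**Stopping rule.** Section 11.2 lists four situations in which the investigator is to discontinue study treatment. The wording is mandatory. The third is that the subject "Is diagnosed with any of the exclusion criteria during the intervention period".

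**Withdrawal rule.** Section 8.4.3 introduces its list with "The following are anticipated conditions/events that would require a subject to be withdrawn from the study". One entry is "Subject develops a condition during the study that violates the inclusion/exclusion criteria". Section 8.4.4 then applies to withdrawn subjects: "Have study treatment returned", but also "Be encouraged to continue coming for regular visits and assessments".

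**Management rule.** Section 10.4, item 3, treats low potassium as an adverse event to be managed: "If mild hypokalemia (3-3.5 mmol/L), to replace with Mist Potassium Chloride and reassess" the level after 3 days; and "If moderate to severe hypokalemia (<3 mmol/L), to assess for symptoms and consider admission for close monitoring, ECG and oral/IV potassium replacement". Withdrawing treatment, prednisolone above all, is only to be considered, and only if the problem does not respond. Item 4 is similar for diabetes: repeat the glucose tests, consider oral glucose-lowering drugs once confirmed, and consider discontinuing for severe uncontrolled hyperglycaemia or an emergency admission.

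**What study treatment means.** Sections 9.1.1 and 9.1.2 define it as the adjunct together with carbimazole and propranolol. For Group 3, section 9.1.3 calls the same two drugs standard treatment.

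**The concern.** One laboratory value triggers two incompatible instructions. At a potassium of, say, 3.3 mmol/L, sections 11.2 and 8.4.3 end study treatment and participation, while section 10.4 gives potassium, rechecks in 3 days and carries on. Section 14.4 allows no deviation without prior ethics approval outside an emergency, so a site following either section can be said to have departed from the other.

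The conflict is likely to arise in practice. Electrolytes and glucose are scheduled at weeks 2, 4 and 6, and section 10.1.1 lists hypokalaemia and diabetes among the events to be collected. Section 6.1 names altered glucose tolerance among the common effects of prednisolone. It also links steroids to renal potassium loss and to case reports of thyrotoxic periodic paralysis. Both events are therefore most to be expected in Group 2.

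At stake are patient safety and consistent exposure across the three sites. Patients enter with FT4 above 1.5 times the upper limit, and the literal stopping rule removes the trial's antithyroid drug and beta-blocker along with the adjunct. The per-protocol analysis planned in section 13.2.2 could also be touched, but its membership rules are not given, so this cannot be taken further.

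**Working it through.** The plan gives no figure on this point. The check is a comparison of the rules, followed by the dose arithmetic for one timing.

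**1. Where the rules overlap.** Of the events that section 10.4 manages, four correspond to an exclusion criterion in section 8.4.2:

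| Event in 10.4 | Exclusion criterion | Action under 11.2 item 3 | Action under 10.4 | Agree? |
|---|---|---|---|---|
| Pregnancy | 3 | Stop | Stop | Yes |
| Thyroid storm | 19 | Stop | Stop | Yes |
| Hypokalaemia | 18 | Stop | Treat; consider stopping if refractory | No |
| Diabetes | 4 | Stop | Confirm, treat; consider stopping if severe | No |

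Hypothyroidism is stopped under both 10.4 and 11.2 item 4, so it raises no conflict. For potassium the overlap is complete: every value below 3.5 mmol/L, including those below 3, meets exclusion 18 and also falls in one of the two bands of 10.4. For diabetes the clash is a little less direct, because exclusion 4 is worded as a history; but 11.2 speaks of a diagnosis made during the intervention, and a newly confirmed diabetes fits that.

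**2. Is there a precedence rule?** The nearest text is the opening of section 10.4, which leaves the treatment of an adverse event to the investigator alone. It does not mention 11.2 or 8.4.3. No other section ranks the rules or exempts either event.

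**3. When a scheduled test could cost doses.** Potassium is scheduled at weeks 2, 4 and 6. Assigned dosing ends at week 4, so only the week-2 scheduled result can shorten it.

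**4. Doses lost if all study treatment stops at the week-2 visit** (daily doses from section 8.1; assumption: exactly 14 of 28 days taken).

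- Carbimazole: 30 × 28 = 840 mg planned; 30 × 14 = 420 mg received; 50% lost.
- Propranolol: 2 × 40 = 80 mg/day; 80 × 28 = 2,240 mg; 80 × 14 = 1,120 mg; 50% lost.
- Cholestyramine: 2 × 4 = 8 g/day; 8 × 28 = 224 g; 8 × 14 = 112 g; 50% lost.
- Prednisolone: 7 × (30 + 20 + 10 + 5) = 455 mg planned; 7 × (30 + 20) = 350 mg received; 7 × (10 + 5) = 105 mg lost; 105/455 = 23%.

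Under 10.4 the same patient would normally complete all of these, unless the investigator judged the problem refractory. An unscheduled test on another day would give different losses.

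**The case against.** The strongest reply is that section 10.4 is plainly the operative rule. It grades its actions event by event: where stopping is wanted (pregnancy, hypothyroidism, thyroid storm) it says so, and for hypokalaemia and diabetes it deliberately uses softer wording. The literal reading of 11.2 also proves too much, since exclusion 14 is current use of cholestyramine or prednisolone, which Groups 1 and 2 take by design. Sites must already read these lists with sense. And 10.4 gives the investigator discretion over treating adverse events.

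Most of this stands as evidence of intent, and it makes 10.4 the likelier rule. It does not remove the conflict. The discretion covers how an event is treated and does not lift the mandatory wording of 11.2 or 8.4.3.

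Four stronger readings are tempting, and the documents do not support them:

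- *Patients would be left without antithyroid therapy.* The text stops trial treatment. Nothing bars routine carbimazole afterwards: section 9.1.1 describes the trial dose as in line with local practice, and 10.4 provides for other appropriate care to be arranged. In Group 3, coverage by 11.2 is by implication only.
- *The primary result is compromised.* Sections 8.4.4 and 11.2 encourage continued attendance, and the week-2 thyroid sample is drawn at the same visit as the potassium. No event rate is given from which a bias could be calculated.
- *Stopping prednisolone at week 2 is an adrenal hazard.* Section 6.1 does rely on tapering, and the stop would be from 20 mg/day. But its concern is prolonged use, an early stop shortens exposure, and the week-6 visit looks for adrenal insufficiency. This is a clinical question that the documents do not settle.
- *Affected patients typically lose half their treatment.* That holds only for a stop at the week-2 visit, and not for prednisolone even then.

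**Conclusion.** The conflict is real and lies in the current text. For on-treatment potassium below 3.5 mmol/L, and for newly detected diabetes, 11.2 item 3 and 8.4.3 literally require stopping and withdrawal, while 10.4 requires management with stopping as an option. Section 10.4 is probably what was meant, but no sentence says so, and the literal alternative would stop trial carbimazole and propranolol for a correctable laboratory value.

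The number of patients affected is unknown. The effect on the intention-to-treat comparison is likely small; that is a judgement resting on the provisions for continued follow-up, not a calculation. The dose losses in the working are the size of the difference between the two rules for one patient stopped at week 2, assuming full adherence until then. The point should be fixed for safety and for consistent exposure between sites. It does not threaten the trial's main conclusion.

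**What to change.** 1. In 11.2 item 3 and the matching entry in 8.4.3, add: *except hypokalaemia and hyperglycaemia, which are managed under 10.4*.
2. State in the same places that stopping study treatment for either event does not by itself mean withdrawal from the study.
3. Ask the sponsor's clinical team to decide, and the protocol to record, whether only the adjunct stops when treatment is stopped for these events, and how prednisolone is to be stopped. These are clinical choices and are not needed to reconcile the sections.

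The cost is a wording amendment with ethics committee approval and notice to the three sites. It adds no patients, visits or tests.
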